Biochemical parameters according to clinical practice will be analyzed at the laboratories of Maggiore della Carità Hospital in Novara and at the laboratories of Giovanni XXIII Children's Hospital in Bari by estimation with Siemens Advia 2400 Healthcare Diagnostics, Siemens ADVIA chemistry XPT and in accordance with the respective protocols of reagent use.

Metaproteomic and metabolomics analysis will be conducted on stool, plasma and urine samples stored during the study for omics signature designation. Metaproteomic analysis with UPHLC-MS/MS mass spectrophotometer will be performed on stool samples to identify the presence of microorganisms in the gastrointestinal tract to be then correlated with the diet followed and clinical parameters of the patients. Peptides identified by the analysis will be entered into the UniProtKB, KEGG database and used for phylogenetic analysis.

Metabolomic analysis will be carried out on all three types of samples; metabolomics conducted on fecal samples will allow assessment of the functional activity of microorganisms, characterizing the intermediate phenotype that mediates host-microbiome interactions. Using one-dimensional gas chromatograph coupled with mass spectrometer (GC-MS-SPME), the metabolic profile and changes in metabolite levels in association with fructose intake will be identified. The identification of the main SCFAs will be carried out with the same instrument and then confirmed by injecting the appropriately treated samples into the instrument, comparing the retention time and the corresponding spectra obtained from GC-MS analysis. This method allows a metabolomic signature to be defined in relation to fructose consumption.

SAMPLE SIZE AND STATISTICAL METHODS

The study plans to enroll 100 children afferent to the centers previously listed. Given a first-type error of 0.05, a power of 80%, a variance of equal fructose consumption in the groups of children with and without NAFLD of 9.53 (pooled variance obtained from data reported in the article by Nier et al. (20), a ratio of 1:3 between children with and without NAFLD (expected prevalence in overweight and obese children ~24% (21)), the sample size will allow to highlight as statistically significant a minimal difference in the averages of fructose consumption between healthy and diseased children of 2.02 grams.

Statistical analysis

Evaluation of the relationship between fructose and NAFLD

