Descriptive statistics will be calculated in order to summarize the sociodemographic, perceptual, anthropometric, dietary, clinic-auxological, anamnestic and laboratory characteristics of the children included in the study.

Categorical variables will be summarized by absolute frequencies and percentages while numerical variables as mean and standard deviation (SD) or median and interquartile range (Q1-Q3) if not normally distributed according to the Shapiro Wilks test and quantile plot observation. The chi-square test or the corresponding nonparametric Fisher's test will be used to test the association between categorical variables and the presence of NAFLD while the t-test or the Mann-Whitney test will be used to test the difference in fructose consumption between children with NAFLD and those without the disease as well as the presence of differences between the two groups for the other numerical variables. The positive false discovery rate method will be used to account for the presence of multiple tests. Based on the number of NAFLD events observed, stratified analysis by age group (preschool age vs. adolescents) and center will be evaluated. **Regarding the assessment of bone metabolism, mean and standard deviation (SD) or median and interquartile range (Q1-Q3) of the parameters provided by the QUS overall and separately for high and low fructose consumption (below vs above median consumption) will be calculated.**

Microbiota analysis

Initially, an exploratory analysis of the relative abundance of the genera of bacteria in the microbiota will be carried out. The relative abundance of each species detected in the fecal samples will be represented by heatmaps. Next, a beta-diversity analysis will be performed comparing the complexity of genera

between subjects. Specifically, three matrices will be created based on weighted and unweighted Bray-Curtis and Unifrac distances that will be used to perform a principal coordinate analysis to highlight the presence of subject clusters based on the complexity of their microbiota.

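### The only powered comparison, fructose intake by NAFLD status, is an unadjusted test pooling ages 3-6 and 12-16 and two enrolling units, with no committed adjustment for age group or centre

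*Combined protocol and SAP*

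**What the plan says.** The Study Design section says that the first phase is cross-sectional and exists to relate fructose consumption to NAFLD. Two of the three units enrol. The inclusion criteria admit children aged 3 to 6 and adolescents aged 12 to 16. Neither the age split nor the centre split of the 100 subjects is given.

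The sample size section starts from "Given a first-type error of 0.05, a power of 80" per cent. It uses a variance of 9.53 ("pooled variance obtained from data reported in the article" cited there) and a 1:3 ratio based on "expected prevalence in overweight and obese children ~24" per cent. It concludes that "the sample size will allow to highlight as statistically significant a minimal difference in the averages of fructose consumption" of 2.02 g.

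The Statistical analysis section, under the relationship between fructose and NAFLD, says that "the t-test or the Mann-Whitney test will be used to test the difference in fructose consumption between children with NAFLD" and those without. The same tests apply to "as well as the presence of differences between the two groups for the other numerical variables". On multiplicity: "The positive false discovery rate method will be used to account for the presence of multiple tests". On age and centre, the only sentence is: "Based on the number of NAFLD events observed, stratified analysis by age group (preschool age vs. adolescents) and center will be evaluated". The text available for review contains no regression or other adjusted model for this comparison.

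**The concern.** This is an observational comparison across ages at which both diet and liver fat may differ. Suppose adolescents eat more fructose and also have more NAFLD. The NAFLD group then holds more adolescents, and its mean intake is higher even if fructose and NAFLD are unrelated within each age band. If the higher-prevalence band eats less, a real association is hidden. Enrolling unit can act in the same way.

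The stratification sentence names the right two factors but does not settle the matter. It gives no threshold, does not say whether cases are counted in total or per stratum, and gives no rule for combining strata. Comparing other variables by NAFLD status may reveal an imbalance but does not correct the fructose result. False discovery rate control deals with the number of tests, not with bias.

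At stake is the main result of the first phase. Under Expected Results, the protocol intends statistically significant findings to feed preventive communication.

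**Working it through.** **1. The plan's own figure.** Inputs from the sample size section: variance 9.53 (SD = √9.53 = 3.087 g), 25 with and 75 without NAFLD, alpha 0.05. Sidedness is not stated; two-sided reproduces the figure.

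- Standard error = 3.087 × √(1/25 + 1/75) = 0.713 g; 2.02/0.713 = 2.83.
- Noncentral t on 98 df: power 80.1% at 2.02 g; minimum detectable difference 2.017 g.
- At 24:76: minimum detectable difference 2.045 g; power 79.0% at 2.02 g.

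So 2.02 g is correct, as the figure for an unadjusted pooled two-group t-test.

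**2. Bias of the crude difference.** Let D be the adolescent-minus-preschool gap in mean intake, and p_P and p_A the two prevalences. With equal numbers per band and no true effect:

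bias = D × [p_A/(p_A + p_P) − (1 − p_A)/(2 − p_A − p_P)]

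For 16%/32%: 0.32/0.48 − 0.68/1.52 = 0.667 − 0.447 = 0.219 g per gram of gap.

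**3. False positives.** Assumed, not in the documents: 50 per band, 24% NAFLD overall, within-band variance 9.53, normal intake, D of 2 to 5 g (0.65 to 1.62 of the planning SD), centre split 50/50 at random. Simulated with N = 100, raw p < 0.05, before any false discovery rate step. Rates are good to about a point.

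| Preschool/adolescent prevalence | Bias per g | Bias, D = 2 to 5 g | Share of 2.02 g | Crude t-test false positives, D = 2, 3, 5 g |
|---|---|---|---|---|
| 24%/24% | 0 | 0 g | 0% | about 5% |
| 20%/28% | 0.110 | 0.22-0.55 g | 11-27% | 6, 7, 9% |
| 16%/32% | 0.219 | 0.44-1.10 g | 22-54% | 9, 13, 21% |
| 10%/38% | 0.384 | 0.77-1.92 g | 38-95% | 17, 30, 56% |

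Linear regression on NAFLD, age group and centre with HC3 robust errors gave about 4-5% throughout. That holds by construction, since no other confounder was simulated. Mann-Whitney rates were within about 2 points of the t-test.

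**4. Sensitivity.**
- If 9.53 is the total variance (within-band variance 9.53 − D²/4), crude rates at 2 and 5 g are 6 and 12%, 9 and 33%, and 19 and 78% in the three unequal rows.
- With 70% adolescents and overall prevalence held at 24% (18.4/26.4, 12.8/28.8 and 4.4/32.4), they are 6-8%, 8-16% and 13-44%.
- With centre as the only confounder (16%/32% by centre, 2-3 g gap), the crude rate is 9-13% and the adjusted rate 5%.

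**5. Masking.** Let the higher-prevalence band eat 2 g less, with a true difference of 2.02 g. Crude power is 65%, 53% and 37% in the three unequal rows; adjusted power with HC3 is 75%, 74% and 71%.

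**6. Separate stratum tests.** One age band or one centre, at 12.5 with and 37.5 without NAFLD, has a minimum detectable difference of 2.88 g and 50% power for 2.02 g.

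**7. The trigger.** With assumed thresholds and binomial counts, at least 20 cases in total has probability 85-87% in every row. At least 8 in each band has probability 88%, 80%, 56% and 12% down the table. On the per-band reading, stratification becomes least likely where it matters most; on the total reading it does not.

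**The case against.** The strongest reply is that the plan already names age group and centre, and a within-stratum comparison does remove confounding by the stratifying factor. If the trigger counts total cases, it would probably be met. That is fair: the remedy is uncommitted, not absent. But a reader cannot tell whether it will be used, and separate strata have only about half the power needed.

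A second reply is that the size is wholly assumed. This also stands. Bias needs both intake and prevalence to differ, the mild case gives only 6-9%, and the largest figures need a nearly fourfold prevalence ratio and a 5 g gap. None of these figures is evidence about this study; they show that the plan's validity depends on a balance it neither states nor checks.

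A third is that the model is partly a matter of choice: a stratified test combined over strata, or logistic regression of NAFLD on intake, would also adjust. That is true. The essential point is to commit to one such analysis. The linear model is suggested because it keeps the difference in grams on which the study was sized. It does assume a common difference in both age bands.

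**Conclusion.** The concern holds and should be fixed. The powered comparison is unadjusted, and adjustment for age group or centre is left to an undefined condition. That follows from the text with high confidence.

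The size is not known. Under the assumptions above, the crude false-positive rate runs from about 5% with equal prevalence to 56% in the most extreme main scenario, and power can fall to 37% when the confounding opposes a true 2.02 g difference. The stated 2.02 g is not an error, but it describes the crude test only.

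**What to change.** In the Statistical analysis section, make the main analysis a linear regression of fructose intake in grams on NAFLD status, age group (3-6 vs 12-16) and enrolling unit (unit 1 Novara vs unit 2 Bari, since three clinics are listed). Fix HC3 robust errors in advance. With adolescent SD 1.5 times preschool SD and a 3 g gap, model-based errors gave 5.0-7.0% false positives and HC3 4.3-4.8%. Report the adjusted difference with its 95% CI, and run the model whatever the number of NAFLD cases. Keep the crude test as descriptive and stratified results as secondary. As a side matter, state whether the main p-value lies inside the false discovery rate family; sizing at 0.05 fits a single test outside it. In the sample size section, say that 2.02 g refers to an unadjusted comparison.

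The cost is wording only: age group and enrolling unit are known for every child. With within-band variance 9.53, power for 2.02 g is about 70-77% with HC3 (73-78% with model-based errors), against 80% planned and 79% crude at 24:76. The 79% assumes no age gap. A 2 g gap adds D²/4 = 1 to the crude variance, and at equal prevalence crude power is then about 74% against 75% adjusted, so the loss can vanish. Other confounders would remain.

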- Quantitative and qualitative analysis of bone composition using quantitative ultrasonography (QUS). This instrument provides different parameters related to bone composition, specifically speed of sound (SOS) assessing bone density, broadband ultrasound attenuation (BUA) assessing trabecular structure, ultrasound peak amplitude assessing trabecular size, number of peaks assessing connectivity of the mineralized matrix structure, and fast wave energy and amplitude assessing elasticity.
- US ultrasound of the abdomen to evaluate hepatic steatosis, perivisceral and subcutaneous fat. The presence of hepatic steatosis (NAFLD) will be classified from stage 1 to stage 3 according to literature (19).

Clinic-auxological evaluation

- Anthropometric measurements, such as weight, height and BMI assessment according to STANDARD DEVIATION SCORE (SDS). Waist and hip circumference measurements.
- Measurement of blood pressure and heart rate.
- Analysis of body composition by bio-impedance analysis (BIA)

Laboratory evaluation, hematochemical assays

Subjects will undergo the following assessments after at least 12 hours of overnight fasting:

- OGTT (glucose-loading curve; glucose 1.75 g/kg per os at time 0', maximum dose 75 g), with basal and every 30 min blood glucose and insulin draws.
- Basal blood draw for c-peptide, AST, ALT, gamma-GT, fractional and total bilirubin, azotemia, creatinine, eGFR, HbAic, fructosamine, total cholesterol, HDL, triglycerides, TSH, FT3 and FT4, leptin, adiponectin, DPP4, uric acid.
- Basal blood sampling for PCR, advanced glycation products (AGEs), AGE receptor (RAGE) and advanced protein oxidation products (AOPPs),
- Basal blood sampling for assay of intermediate products of fructose metabolism (fructose-lysine)
- Calcium, phosphorus, 25-OH vitamin D, PTH, osteocalcin, RANKL, osteoprotegerin, bone isoenzyme alkaline phosphatase, telopeptide C-terminal collagen type I (CTX), intact procollagen amino terminal type 1 (P1NP), IL-6, IL-1beta, biochemical parameters needed to assess bone metabolism.

They will, in addition, be performed:

- A urinalysis and 24-hour urine collection for evaluation of fructose metabolites in urine.
- Fecal sample for metabolomics and metaproteomic analysis.

ANALYSIS BY BIOCHEMICAL, HORMONAL AND MASS SPECTROMETRY PARAMETERS

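### The NAFLD comparisons pool ages 3-6 and 12-16 without adjustment, so a difference in age mix can be reported as a difference linked to NAFLD

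*Combined protocol and SAP*

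**What the plan says.** Inclusion criteria admit two separate age bands, 3 to 6 and 12 to 16 years. Neither that section nor Subjects sets a quota for either band. Recruitment is at clinics in Novara and Bari.

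Under Statistical analysis, in the part on fructose and NAFLD, "the t-test or the Mann-Whitney test will be used to test the difference in fructose consumption between children with NAFLD" and those without it, "as well as the presence of differences between the two groups for the other numerical variables". No regression model or covariate appears in the statistical section. Age and centre enter in one sentence: "Based on the number of NAFLD events observed, stratified analysis by age group (preschool age vs. adolescents) and center will be evaluated". The only other correction concerns multiplicity: "The positive false discovery rate method will be used to account for the presence of multiple tests".

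Sample size and statistical methods sizes the study for the same pooled two-group comparison, able to detect "a minimal difference in the averages of fructose consumption between healthy and diseased children of 2.02 grams".

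On scales, Clinic-auxological evaluation has "Anthropometric measurements, such as weight, height and BMI assessment according to STANDARD DEVIATION SCORE (SDS). Waist and hip circumference measurements" and then "Measurement of blood pressure and heart rate". Standard deviation scores are attached to weight, height and BMI. No age-standardised scale is given for waist, hip, blood pressure, heart rate or bio-impedance, nor for laboratory values such as creatinine. Routine biochemistry is measured in two hospital laboratories ("Hospital in Novara and at the laboratories of Giovanni XXIII").

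**The concern.** Many of the measures change as a child grows, and the design leaves a gap of six years between its two age bands. If NAFLD is more common in one band, the NAFLD group holds a larger share of that band than the comparison group does. The pooled test then picks up part of the age difference and attributes it to NAFLD. Centre works in the same way if both NAFLD prevalence and measured values differ between Novara and Bari.

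False discovery rate control does not help here. It limits chance findings among many tests, but a p-value distorted by age stays distorted after the correction.

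The fructose comparison is the only one with a power calculation. Study design also makes differences in clinical, auxological and blood parameters by disease status a purpose of the cross-sectional part, and Expected results looks for new markers and for preventive messages based on significant findings. A marker of age reported as a marker of NAFLD would mislead both uses.

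**Working it through.** **Inputs from Sample size and statistical methods:** N = 100, ratio 1:3 (25 with and 75 without NAFLD), variance of fructose consumption 9.53 within each NAFLD group, alpha 0.05, power 80%, expected prevalence about 24%.

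**Step 1: the plan's own figure.** SD = √9.53 = 3.087 g. The normal approximation gives (1.960 + 0.842) × 3.087 × √(1/25 + 1/75) = 1.997 g. The noncentral t distribution, two-sided, gives 2.017 g. The stated 2.02 g reproduces, and it belongs to an unadjusted comparison of two groups pooled over age.

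**Step 2: the mechanism.** With no NAFLD effect within either band, the expected pooled difference is (a₁ − a₀) × gap. Here a₁ and a₀ are the adolescent shares among children with and without NAFLD, and the gap is the difference in means between bands. For a 50/50 split:

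- Prevalence 24% vs 24%: a₁ = a₀ = 0.50, so there is no bias.
- 18% vs 30%: a₁ = 0.5 × 0.30/0.24 = 0.625; a₀ = 0.5 × 0.70/0.76 = 0.461; difference 0.164.
- 12% vs 36%: a₁ = 0.5 × 0.36/0.24 = 0.750; a₀ = 0.5 × 0.64/0.76 = 0.421; difference 0.329.

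**Step 3: how often the pooled test rejects when nothing is there.** Assumptions not in the documents: overall prevalence 24%, gap of 1 to 2 within-band SDs, equal SDs, higher prevalence in adolescents, three age splits. Prevalences follow from p₁ = 0.24/(w + r(1 − w)) and p₂ = r × p₁, where w is the preschool share and r the prevalence ratio. The rejection rates are simulated, for one two-sided t-test at 5% before any false discovery rate step.

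| Preschool/adolescent | Ratio | Prevalence | a₁ − a₀ | Pooled test rejects |
|---|---|---|---|---|
| any of the three | 1 | 24% vs 24% | 0 | about 5% |
| 20/80 | 1.67 | 15.7% vs 26.1% | 0.09 | 6-9% |
| 50/50 | 1.67 | 18% vs 30% | 0.16 | 9-17% |
| 80/20 | 1.67 | 21.2% vs 35.3% | 0.12 | 8-14% |
| 20/80 | 3 | 9.2% vs 27.7% | 0.16 | 9-17% |
| 50/50 | 3 | 12% vs 36% | 0.33 | 23-53% |
| 80/20 | 3 | 17.1% vs 51.4% | 0.30 | 23-53% |

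A linear model with NAFLD status, age band and centre rejects in about 5% in every row.

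Hand check of one top cell (50/50, ratio 3, gap 2 SD). The bias is 2 × 0.329 = 0.658 SD. The variance within NAFLD groups is 0.24 × (1 + 4 × 0.75 × 0.25) + 0.76 × (1 + 4 × 0.421 × 0.579) = 1.92. The standard error is √(1.92 × (1/24 + 1/76)) = 0.324. The ratio is 2.03, so the rejection rate is about Φ(2.03 − 1.96) = 53%.

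**Step 4: precision at equal prevalence.** At a 50/50 split, pooling adds 0.25 × gap² to the within-group variance. The unadjusted interval is wider by √(1 + 0.25 × 1) = 1.12 at a gap of 1 SD and by √(1 + 0.25 × 4) = 1.41 at 2 SD.

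**Step 5: price of adjustment when a measure is unrelated to age.** At a 50/50 split, age band alone multiplies the variance of the NAFLD estimate by 0.24 × 0.76/[0.5 p₁(1 − p₁) + 0.5 p₂(1 − p₂)]. This is 0.1824/0.1788 = 1.02 at 18% vs 30%, and 0.1824/0.1680 = 1.09 at 12% vs 36%.

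**The case against.** The strongest reply is that the authors saw the issue. They name age group and centre as stratifiers, and with about 24 NAFLD cases over two bands and two centres (about six per cell if evenly spread) it is prudent to make stratification depend on the number of cases. That is fair. What remains is that no threshold is given, no combined age-adjusted estimate is planned, and nothing says which result prevails if pooled and stratified results disagree. When cases are few, the plan falls back on the unadjusted test. An adjusted model does not need enough cases in every cell.

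Second, the documents show no bias. They give one overall prevalence and nothing by band. This stands: a reader might infer that the planned results will be false, and the documents do not support that. They also fix no age split, and the size depends heavily on it, as the 20/80 rows show.

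Third, a reader might turn the argument into grams of fructose by taking 9.53 as the variance within an age band, and conclude that a gap of several grams between bands could produce the whole 2.02 g. The plan uses 9.53 as the variance within each NAFLD group, so that step is inconsistent with it. At a 50/50 split and equal prevalence, gaps of 4 or 6 g would raise the within-group variance to 9.53 + 0.25 × 16 = 13.53 or 9.53 + 0.25 × 36 = 18.53, and the detectable difference to about 2.4 or 2.8 g. On the plan's own reading, a 6 g gap would leave a within-band variance of only 9.53 − 9 = 0.53. No size in grams is therefore claimed here.

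Fourth, centre biases the comparison only if NAFLD prevalence differs by centre as well as measured values. No figure bears on this, so centre is in the model as a precaution. Finally, the chi-square and Fisher comparisons and the LEfSe analysis are also unadjusted for age; this point does not cover them.

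**Conclusion.** The concern holds as a defect of the planned analysis. Followed as written, the plan can report an age difference as a NAFLD difference, for fructose in grams and for any other numerical variable that is not age-standardised. Whether it will do so is unknown. With no true effect, overall prevalence of 24% and a gap between bands of 1 to 2 within-band SDs, a nominal 5% pooled test rejects in about 5% of studies at equal prevalence, 6-17% at a ratio of 1.67 and 9-53% at a ratio of 3, over the three age splits. The upper end needs the threefold ratio, the 2 SD gap and a split of 50/50 or 80/20 together. At equal prevalence the only loss is precision. Measures expressed as age-standardised scores are largely protected. The 2.02 g figure is correct for the unadjusted test it describes. The change is worth making before analysis because it is cheap and the alternative rests on an unknown.

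**What to change.** Under Statistical analysis, make the main comparison for fructose and the other numerical variables a linear model with NAFLD status, age band and centre. Sex and age within band may be added. Use robust standard errors, or a log scale for positive skewed variables. For variables that remain non-normal, or that can be zero or negative (standard deviation scores, for example, cannot be logged), use a van Elteren test stratified by age band. Apply the false discovery rate method to the adjusted p-values. Keep the results stratified by age group and centre as support where the number of cases allows.

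The cost is plan wording and a few degrees of freedom. Age and centre are already known for every child, so no visit or procedure is added. If a measure is unrelated to age, a little precision is lost. Using the 50/50 variance factors from the working, the detectable fructose difference would move from 2.02 g to about 2.02 × √1.02 = 2.04 g at 18% vs 30%, or 2.02 × √1.086 = 2.10 g at 12% vs 36%, for age band alone. Where a measure does differ between bands, removing that variation offsets the loss and can outweigh it.

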Reduced phosphate uptake, on the other hand, depends on the depletion of phosphate groups by a specific isoform of phosphofructokinase expressed by enterocytes (13); therefore, the reduction in the ATP/AMP ratio leads to inhibition of the Na/P transporter. This mechanism would also occur at the renal level where inhibition of this transporter promotes urinary excretion of phosphorus (14).

Recent studies show how an increase in dietary fructose appears to be responsible for the onset of several obesity-associated diseases; foremost among them NAFLD, which is increasing in tandem with obesity even in the pediatric population. The aim of this study is mainly to understand the effect of fructose on the molecular events contributing to pediatric development, as this could be an important target to address the clinical and social problems arising from its prevalence in pediatric age.

AIMS OF THE STUDY

The primary aim of this study is to evaluate the effects of fructose intake in a group of preschool children and overweight or obese adolescents; in particular, to investigate the impact of fructose consumption in the development of liver complications, such as NAFLD, and its degree of severity, as well as its impact in other obesity-associated diseases. **In addition, the present study aims to describe the composition of bone metabolism according to the level of fructose consumption.** Secondly, by means of omics analysis (metabolomics and metaproteomic), the aim is to characterize the microorganisms present in the gastrointestinal tract and their microbial activity in relation to dietary habits, fructose intake and clinical parameters. Finally, sociodemographic and cultural factors, in the children and adolescents considered in the study, and in their families, will be surveyed.

STUDY DESIGN

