This study consists of two parts, the first phase involves the conduct of a cross-sectional study to assess the relationship between fructose consumption and the presence of NAFLD and the difference in several parameters, including anamnestic, clinical, auxological and hematochemical assays and the presence of the disease, and a second prospective part for the sociological evaluation one year after entering the study. It constitutes an extension of a study already approved by the University of Bari, approval of which is attached by the Independent Ethics Committee university hospital company "Consorziale Policlinico" with approval number CE/7331. The study involves the collaboration of three different units, respectively formed by the University of Eastern Piedmont (unit 1), University of Bari "A. Moro" (unit 2) and the University of Rome "Foro Italico" (unit 3). The first two units will enroll subjects with criteria of interest for the study. The University of Rome, on the other hand, will be concerned with the socioeconomic aspect of the study with the preparation of ad hoc questionnaires to be submitted to both children/adolescents and families.

Subjects

100 overweight or obese preschool children and adolescents visited at the Outpatient Clinic of Pediatric Endocrinology of the AOU Maggiore della Carità in Novara, at the Transition Endocrinology Outpatient Clinic of the SCDU Endocrinology and at the Outpatient Clinic of Pediatric Endocrinology "B.Trambusti" of the Giovanni XXIII Pediatric Hospital in Bari will be included in the study. Subjects will be selected continuously with adherence to the inclusion criteria from January 2024 until the end of December.

Inclusion criteria

- Children and adolescents with expression of informed consent according to art.2 quinque of Legislative Decree n.196/2003;
- Preschool children of both sexes aged 3 to 6 years and adolescents of both sexes aged 12 to 16 years;
- Children diagnosed with overweight (defined by BMI > 97th percentile for children younger than 5 years; and BMI > 85th percentile for children older than 5 years) or obesity (defined by BMI > 99th percentile for children younger than 5 years; and BMI > 97th percentile for children older than 5 years) (15,16).

Exclusion criteria

- Children and adolescents who are not in this age group;
- Children and adolescents with liver disease different than NAFLD;
- Children and adolescents with genetic type obesity or secondary obesity;

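### The bone (QUS) summary by high versus low fructose splits at an unqualified median with no age breakdown, in a sample made up of two separate age bands

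*Combined protocol and SAP*

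**What the plan says.** The Aims section states that "the present study aims to describe the composition of bone metabolism according to the level of fructose consumption". The analysis serving that aim is the last sentence under Evaluation of the relationship between fructose and NAFLD: means with SD, or medians with quartiles, of "the parameters provided by the QUS overall and separately for high and low fructose consumption (below vs above median consumption) will be calculated". The median is not qualified as pooled or age-specific.

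The Inclusion criteria admit "Preschool children of both sexes aged 3 to 6 years and adolescents of both sexes aged 12 to 16 years", so nobody between the two bands is enrolled. The split of the 100 children between bands is not given.

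Three other places come near the point:
- The sentence just before the bone sentence reads "Based on the number of NAFLD events observed, stratified analysis by age group (preschool age vs. adolescents) and center will be evaluated".
- The same paragraph plans comparisons between children with and without NAFLD for fructose intake, "as well as the presence of differences between the two groups for the other numerical variables". Bone measures may fall under this, but by NAFLD status and not by fructose level.
- Under Clinic-auxological evaluation, standard deviation scores are stated for anthropometry. None is stated for QUS, of which the Instrumental assessment section says "This instrument provides different parameters related to bone composition".

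**The concern.** Preschool children and adolescents may differ in how much fructose they eat and in their QUS values. Where both are true, one cut across the whole sample puts more of the higher-intake band into the high group. The high and low groups then differ in age mix as well as in fructose. A reader could take an age difference for a fructose difference, or an age difference could hide one.

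This summary is the only stated bone analysis by fructose level. The Expected results section looks for new knowledge on fructose and bone metabolism, so the contrast is likely to be read as a fructose result. With no model or test beside it, the cell summaries are all that a reader has. The effect may also vary by parameter, since the several QUS measures need not share one age gap.

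**Working it through.** **The plan's own figure.** The plan gives no sample size, power or effect figure for QUS. The only figure in the sample-size section is the detectable fructose difference of 2.02 g by NAFLD status. With SD = √9.53 = 3.087, groups of 25 and 75, two-sided 0.05 and 80% power, the noncentral t gives 2.017 g. It reproduces, but has no bearing on this point.

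**Inputs.** From the documents: N = 100, two separate age bands, a median split. Assumed, because the documents are silent: share of adolescents p = 0.3, 0.5 or 0.7; intake gap between bands d = 0, 0.5 or 1 within-band SD; QUS gap between bands q, in within-band QUS SD; normal intake with equal SD in each band; no link between fructose and QUS inside a band. Adolescents are taken as the higher-intake band.

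**Step 1, pooled median m.** It solves p·Φ(d − m) + (1 − p)·Φ(−m) = 0.5. For p = 0.5 and d = 1, m = 0.5.

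**Step 2, age mix of each half.** Share of adolescents in the high half H = 2p·Φ(d − m), and in the low half L = 2p·Φ(m − d). For p = 0.5 and d = 1: H = Φ(0.5) = 0.691 and L = Φ(−0.5) = 0.309.

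**Step 3, share passed through.** s = H − L, and the expected high-low QUS contrast with no fructose effect is s·q.

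| Age mix | d = 0 | d = 0.5 | d = 1 |
|---|---|---|---|
| 50/50 | 0 | 0.599 − 0.401 = 0.197 | 0.691 − 0.309 = 0.383 |
| 30/70 or 70/30 | 0 | 0.165 (16%, unrounded 0.16499) | 0.315 (31%, unrounded 0.31494) |

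Differences are taken before rounding. At 50/50, a QUS gap of 0.5 SD gives a contrast of 0.10 (d = 0.5) or 0.19 (d = 1). A QUS gap of 1 SD gives 0.20 or 0.38. If q = 0 the contrast is 0 whatever d is.

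**Step 4, band-specific medians.** Half of each band falls in each group, so H = L = p and s = 0. The between-band part is removed by construction. Age still varies inside a band. If age correlates r with both intake and QUS within a band, and nothing else links them, the within-band contrast is r² × 2√(2/π) = 1.596·r². That is 0.06 SD at r = 0.2 and 0.14 SD at r = 0.3 (both assumed).

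**Step 5, precision.** Standard error of a high-low difference = √(1/n₁ + 1/n₂) in within-band SD: 25 v 25 gives 0.28; at 30/70, 15 v 15 gives 0.37 and 35 v 35 gives 0.24. For the pooled 50 v 50 contrast it is 0.20 if QUS does not differ by band. With both gaps at 1 SD, the variance inside each half is 1 + 0.691 × 0.309 = 1.213, and √(2 × 1.213/50) = 0.22.

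**The case against.** The strongest reply is that nothing in the documents shows a distortion. It needs a gap in intake and a gap in QUS together, and the documents give neither. That stands: every nonzero figure above is an assumption. Three of the four nonzero contrasts at 50/50 (0.10, 0.19 and 0.20) are also smaller than one standard error of the pooled difference, which is about 0.21 to 0.22 in those cases.

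Second, the aim is to describe, and a crude description is not wrong for being crude. That stands as far as severity goes. It does not remove the point, because this is the only bone description by fructose level and the reader is given nothing with which to see the age mix.

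Third, level of consumption can naturally mean an absolute amount, which a pooled median respects and a band-specific one does not. That also stands, and is why the overall summary should be kept and not replaced.

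Fourth, the plan names age group as a stratifier in the sentence before. A reader might infer that this covers QUS, or, in the other direction, that the authors ignored age. The documents support neither. The stratification depends on the number of NAFLD events, is only to be evaluated, and is not stated for QUS; but it shows that the two-band structure was recognised.

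**Conclusion.** The point holds as a minor one. The summary leaves the median unqualified and states no age breakdown. Under the plain reading of a pooled cut, age is mixed with fructose for any QUS parameter where both gaps exist. The share of the between-band QUS gap carried into the contrast is 0 to 38% at a 50/50 mix and 0 to 31% at 30/70 or 70/30, for assumed intake gaps of 0 to 1 within-band SD.

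A reader might infer more than this in three ways:
- That the bone result is biased. The documents do not show it, and if either gap is absent the distortion from age band is zero.
- That a test or the main NAFLD result is compromised. No test is planned on this summary, and no error rate, power figure or primary result depends on it.
- That splitting by band cures the problem entirely. It removes the between-band part only. Age differences within a band are reduced but may remain.

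**What to change.** Keep the planned overall summary. Add the high-low QUS summaries separately for ages 3-6 and 12-16, cutting at the median intake of that band. State each median in grams, and give the number, mean age and sex distribution of every cell, so that any remaining age imbalance within a band is visible.

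The cost is a sentence or two of analysis-plan wording and a re-cut of data already being collected. There are two real downsides. Cells shrink to about 25 each at a 50/50 mix (about 15 and 35 at 30/70), with a standard error of about 0.28 within-band SD per band at 50/50, against about 0.20 to 0.22 for the pooled contrast. These are two separate contrasts set against one, so the comparison is only a guide. And high comes to mean high for the age group; the retained overall summary and the stated gram values offset this. The wording should be settled before the data are seen, since the present text allows either median.
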